8.4 Responsibilities of the investigator and IRB

The responsibilities of investigators include creation of and maintenance of a core study team (Please refer to Section 7 for more information), adhering to protocol requirements, including

educational requirements for implementation of the intervention in the post-period, and ultimately, are the institutional leads to support protocol implementation. The study team will be responsible for timely reporting, where appropriate, to the institutional IRB. The investigators must demonstrate reasonable efforts to obtain qualified patients for the study.

The responsibilities of the IRB include adhering to institutional requirements, performing an objective review of the acceptability of the study protocol and analysis plan (i.e. research) in terms of institutional requirements, commitments, regulations, applicable law, and professional conduct and practice, provide continued monitoring and review of research, review of key events (protocol amendments, protocol deviations, adverse events, or non-compliance), review of any required progress reports, and to report any required information to appropriate authorities and/or organizations.

8.5 Publication

All data generated in this study are the property of the sponsor. An integrated clinical and statistical analysis report will be prepared at the completion of the study.

Publication of the results by the investigator will be subject to mutual agreement between the investigator and the sponsor and will follow the sponsor's SOP on publications.

9 Protocol deviations and violations

A *protocol deviation* is any change, divergence, or departure from the study design or procedures that is under the investigator's responsibility and oversight (as defined by regulations) without prior written IRB approval or favorable opinion of an appropriate amendment and that does not have a major impact on the subject's rights, safety, or well-being, or on the integrity and authenticity of the study data. Deviations may include, but are not limited to, departure from inclusion/exclusion criteria, dosing, duration of treatment, failure to perform the required assessments at specified time points, scheduling of visits not in accordance with specifications, or subject safety. Deviating from the protocol is permitted only if absolutely necessary for the safety or clinical management of the subjects and will immediately be reported to the sponsor. Protocol deviations will be reported to the sponsor either verbally or electronically within 5 working days from the day of discovery.

A *protocol violation* is a form of protocol deviation that has a major impact on the subject's rights, safety, or well-being, or on the integrity and authenticity of the study data. Protocol violations will be reported to the sponsor within 24 hours, if possible. The IRB will be notified within the time period dictated by the IRB associated with this study.

11.1 Measurement of lesion characteristics

Measurements are to be taken while the infected area is in a nondependent position, e.g., if infection was on the leg, the subject was lying down, not sitting or standing. All types of infections are to be measured as measurement of erythema upon enrollment and any subsequent physical follow-up visits. Maximal dimensions of erythema, both width and length, are to be recorded in centimeters. Investigators should attempt to find the infection edge that best distinguished erythema from non-erythematous skin. Erythema is to be measured in the dimension of maximal length. The maximal width is to be measured perpendicular to the axis of the maximal length. The maximal width measurement does not have to be in the center if the area of erythema is irregular. The length of the infection is to be multiplied by perpendicular width of wound.

HIV	human immunodeficiency virus
HRQoL	health-related quality of life
ICU	intensive care unit
LOS	length-of-stay
LTC	long-term care
MedDRA	Medical Dictionary for Regulatory Activities
MIC	minimum inhibitory concentration
MCS	mental component score
MOS	medical outcomes study
mEq/L	milliequivalents per liter
mmHg	milliliter of mercury
mmol/L	millimolar
mg/dL	milligrams per deciliter
MRSA	Methicillin-resistant Staphylococcus aureus
OPAT	outpatient parenteral antibiotic therapy
PICC	peripherally inserted central catheter
PCS	physical component score
PRO	patient-reported outcome
SAE	serious adverse event
SAP	statistical analysis plan
SAS	statistical analysis system
SD	standard deviation
SF	short-form
SIRS	Systemic Inflammatory Response Syndrome
SNF	skilled nursing facility
US	United States
WHO	World Health Organization
WPAI	Work Productivity and Activity Impairment Questionnaire

1.0 Introduction

This statistical analysis plan (SAP) outlines the planned analysis for data collected within Allergan study CMO-US-ID-0528, entitled "Development of a New Critical Pathway for Treatment of Acute Bacterial Skin and Skin Structure Infections". This SAP applies to the protocol, Version 6.0, dated March 03th, 2017, and provides a description of methods for handling the data.

This pragmatic trial has been developed to assess a new critical pathway for the treatment of acute bacterial skin and skin-structure infections (ABSSSI); it will include the use of guideline-based criteria to identify patients eligible for outpatient parenteral antibiotic therapy (OPAT), and, for those who meet these criteria, the use of dalbavancin — a novel, single-dose, long-acting, second generation lipoglycopeptide indicated for the treatment of ABSSSI caused by susceptible strains of Gram-positive bacteria.

2.0 Study Objectives

2.1 Primary Objective

The primary objective of this study is to estimate the difference in infection-related total admitted hospital days during initial care (the date of enrollment to 10-14 days) and follow-up (30 days after initial care) comparing ABSSSI patients receiving care before implementation of the new critical pathway and after implementation.

2.2 Secondary Objectives

The secondary objectives of this study are to estimate the difference in the following outcomes during initial care (the date of enrollment to 14 days) and follow-up (30 days after initial care) comparing ABSSSI patients receiving care before implementation of the new critical pathway and after implementation:

- Total admitted hospital days during initial care and follow-up
- Infection-related major surgical interventions that required operating room time during initial care and follow-up
- Infection-related hospitalizations during initial care and follow-up
- Infection-related hospitalizations during initial care and follow-up that resulted in admission to Intensive Care Unit (ICU)
- All cause hospitalizations in the 30 days post discharge from the hospital
- Infection-related emergency department (ED) visits during initial care and follow-up
- Infection-related outpatient healthcare visits during initial care and follow-up
- Use of a peripherally inserted central catheter (PICC) line or central line to administer antibiotic therapy during initial care and follow-up
- Infection-related healthcare visits due to PICC line or central line used to administer antibiotic therapy during initial care and follow-up

- Response to treatment at end of treatment visit
- Serious adverse events (SAEs) during initial care and follow-up
- Patient satisfaction with care (patient reported or completed by a caregiver if the patient cannot complete)
- Patient work and productivity loss (patient reported or completed by a caregiver if the patient cannot complete)
- Patient Health-related Quality of Life (HRQoL) (patient reported or completed by a caregiver if the patient cannot complete)

3.0 Study Design

This study will employ a “pre-post” pragmatic design, which will consist of both a pre-period, or an observational baseline period, and a post-period, or an interventional period. The pre-period and post-period will consist of independent groups of patients. During the pre-period, the site will implement the first component of the critical pathway through implementation of guideline-based criteria to identify patients admitted to the hospital, obtain informed consent, and monitor enrolled subjects. The site will initiate treatment for ABSSSI with “usual care,” defined as site- or physician-specific antibiotic treatment of ABSSSI with coverage for a known or suspected Gram-positive infection (e.g., vancomycin, linezolid, and daptomycin) to each study patient who meets all inclusion and exclusion criteria. Blinding of treating physician to patient enrollment in the study during the pre-period will ensure unbiased provision of usual care. During the post-period, for all patients who provide informed consent and are subsequently enrolled, each participating site will additionally implement the second component of the new critical pathway, use of dalbavancin, at the point of care in the hospital or other designated site to each study patient who meets all inclusion and exclusion criteria.

For both periods of interest, patient follow-up spans the period beginning on the day of study enrollment and ends 44 days thereafter, which incorporates an initial care period of 14 days (reflecting the 10–14-day period during which most antibiotics are anticipated to be required for care of ABSSSI) and a subsequent “follow-up” period of 30 days. Study measures will be collected as described in the protocol and will be based on medical records, unless otherwise indicated.

A schedule of assessments is provided in Appendix A. Follow-up visits will be scheduled for approximately 48-72 hours after enrollment (both periods), 10-14 days after enrollment (both periods), and 44 days after enrollment (both periods). Any additional visits to the visit schedule given in Appendix A will be at the discretion of the patient and treating physician.

The duration of the study was not predetermined; it is dependent on the time required to enroll the necessary number of eligible patients (43 patients per time period; 86 patients enrolled in all).

4.0 Study Measures

4.1 Baseline Characteristics

The following baseline characteristics will be collected:

- **Demographic data:** Age (in years, derived and described in Appendix B), gender, ethnicity, race, employment status, and location patient presents from (e.g. from home, long-term care [LTC], skilled nursing facility [SNF], nursing home).
- **Comorbidities:** myocardial infarction, congestive heart failure, peripheral vascular disease, cerebrovascular disease, dementia, chronic pulmonary disease, rheumatologic disease, peptic ulcer disease, mild liver disease, diabetes with/without complications, renal disease, moderate or severe liver disease (Child-Pugh Class B and C), any malignancy (including leukemia and lymphoma), metastatic solid tumor, cancer (active, remitted/cured), alcohol/drug abuse/illicit needle use, malnutrition, human immunodeficiency virus (HIV), other immunocompromising conditions, altered mental status, lymphedema or chronic venous stasis, and peripheral vascular disease.
- **Charlson Comorbidity Index (CCI):** A derived variable based on the presence/absence of the comorbidities specified above. The formula by which the CCI is calculated is detailed in Appendix C.
- **Infection type:** Cellulitis/erysipelas, wound infection, major cutaneous abscess
- **Infection and clinical characteristics during the initial assessment at the hospital and end of treatment visit:**
 - Lesion size and location
 - Pain and tenderness associated with the lesion
 - Fever ($>100.4^{\circ}\text{F}$; $>38.0^{\circ}\text{C}$; or site-specific definition)
 - *Systemic inflammatory response syndrome* (SIRS) (see Appendix B)
 - Blood pressure (BP, in mmHg)
 - Total white blood cell count ($\times 10^9/\text{L}$)
 - Hemoglobin (g/dL)
 - Sodium (mmol/L)
 - Glucose (mg/dL)
 - Serum creatinine (mg/dL)
 - C-reactive protein (mg/dL)
 - Rapid microbial assay
 - Microbiological culture type (i.e. blood, wound swab, urine) and results thereof
 - Presence of recurrent infection and/or any ABSSSI infections in the prior 6 months
- **Utilization of healthcare services in prior 3 months:** Hospitalizations and primary reason, surgical interventions and primary

reason, admission to the ICU and primary reason, ED visits or other outpatient visits (e.g., infusion center and physician’s office) and primary reason, use of dialysis, use of any medications for chronic diseases and specifically use of an antibiotic medication, prior antibiotic treatment failure (determined by discontinuation of treatment due to worsening or recurrent ABSSSI or the occurrence of an adverse event related to the antibiotic), and receipt of wound care for the presenting infection.

4.2 Primary Outcome

The primary outcome (i.e., infection-related total number of days spent in hospital) will be assessed during the 44-day period of interest, including the initial-care period (i.e., beginning on the date of enrollment and ending 14 days thereafter) and the follow-up period (the 30-day period following initial care).

4.3 Secondary Outcomes

Secondary outcomes will be assessed during initial care (the date of enrollment to day 14) and/or follow-up (30 days after initial care), and include:

[figure not shown]
[figure not shown]
Measure	Definition	Period of Assessment
Total admitted hospital days	Total length of stay (LOS) of all hospitalizations during the 44 days of the study (including initial hospitalization)	Initial care and follow-up
Infection-related major surgical interventions that required operating room time	Number of all, unexpected and expected infection-related major surgical interventions that required operating room time	Initial care and follow-up
Infection-related hospitalizations	Number of infection-related hospitalizations	Initial care and follow-up
Infection-related hospitalizations that resulted in admission to ICU	Number of infection-related hospitalizations resulting in admission to the ICU.	Initial care and follow-up
All-cause hospitalizations in the 30 days following discharge from the initial hospitalization	Number of all hospitalizations for patients after initial hospitalization discharge	Overall, including Initial care and follow-up
Infection-related ED visits	Number of all, unexpected and expected infection-related ED visits	Initial care and follow-up

[figure not shown]
Measure	Definition	Period of Assessment
Infection-related outpatient healthcare visits (e.g., physicians' office visits, ED visits, infusion center visits, home health visits)	Number of all, unexpected and expected infection-related outpatient healthcare visits, generated for all patients and repeated by site.	Initial care and follow-up
Use of PICC line or central line to administer antibiotic therapy	Number of PICC line or central line placement for antibiotic therapy	Initial care and follow-up
Infection-related healthcare visits (e.g., hospitalizations, ED visits, other outpatient visits) due to PICC line or central line used to administer antibiotic therapy	Number of all, unexpected and expected infection-related healthcare visits due to PICC line or central line used to administer antibiotic therapy	Initial care and follow-up
Response to treatment at end of therapy visit	Response to treatment will be defined through an assessment of erythema and the absence of fever at 10-14 days and will be categorized as a complete response, partial response, or failure.	Initial care
Serious adverse events (SAEs)	Number of events, number of patients and percentage of patients experiencing SAEs as described in protocol	Initial care and follow-up
Patient satisfaction with care	Summarize patient satisfaction with care (reported by patient, questionnaire provided in protocol). This will be completed by a caregiver if the patient cannot complete.	Follow-up
Patient work and productivity loss	Number of days with lost/reduced productivity, as measured through the Work Productivity and Activity Impairment	Follow-up

Measure	Definition	Period of Assessment
	(WPAI) questionnaire. This will be completed by a caregiver if the patient cannot complete.	
Patient HRQoL	Patient reported, as measured through the SF-12 ¹ (short-form), with acute recall (1-week recall). This will be completed by a caregiver if the patient cannot complete.	Initial care (in person) and follow-up (in person). Change scores calculated for initial care

Healthcare resource usage during the three months prior to the study will be based on examination of the patient’s medical records.

4.6 Safety

At each visit, patients will be queried regarding adverse events (AEs) and SAEs, and medication errors that occurred since the previous visit. Specifically, patients will be asked to volunteer information with a non-leading question such as, "How do you feel since your last visit?" Study site personnel will record all pertinent information in the patient's case report form (CRF), as described in details in the protocol.

5.0 Changes in the Protocol Specified Analyses

Infection characteristics described in the protocol including hyperglycemia (>120mg/dL blood glucose or site-specific definition), thrombocytopenia

($<150,000$ platelet count or site-specific definition), acidosis (<7.35 pH of the blood or site-specific definition or described in medical chart), hyponatremia (<135 mEq/L blood sodium or site-specific definition), uremia (as described in medical chart), and anemia ($14-18$ g/dL hemoglobin for men or $12-16$ g/dL hemoglobin for women or site-specific definition) will not be derived from laboratory values or reported in analysis.

The protocol specifies that the Mann-Whitney U test will be utilized for comparison of continuous variables in analyses. However, it was later determined that the t-test offers better power and easier inference in most moderate to large sample size situations where assumptions of the t-test are not grossly violated. Therefore, the t-test where possible and reverting to non-parametric alternatives only in special circumstances. The rationale for this change is as follows:

- The sample size estimate in the protocol is based on a t-test. As the study is powered for a t-test, it would be most appropriate to use a t-test if possible.
- T-tests are generally equally or more powerful than Mann-Whitney U tests if the sample size is moderate or large, even if the normality assumption is not met². Non-parametric tests may not have adequate power to detect differences for the sample.
 - Per Lumley *et al.*²: "In small samples most statistical methods do require distributional assumptions, and the case for distribution-free rank-based tests is relatively strong. However, in the large data sets typical in public health research, most statistical methods rely on the Central Limit Theorem, which states that the average of a large number of independent random variables is approximately Normally distributed around the true population mean. It is the normal distribution of the average that underlies the validity of the t-test..."
 - The sample size is sufficient to meet this criterion even if the data are right-skewed. This assumption will be reassessed if the data are extremely non-normal.

6.0 Statistical Plan and Methods

As the data are analyzed, some deviations from expectations and/or assumptions will become apparent (e.g., missing data, distributional assumptions, and small sample sizes in some subgroups of interest). In instances where these deviations would make the proposed analyses inappropriate/infeasible and/or difficult to interpret, modifications to the analysis plan will be made accordingly, and noted in the final report.

6.1 General Considerations

6.1.1 Analysis populations

Enrolled Set

The enrolled set consists of all patients who have signed informed consent and met all study eligibility criteria. Data will be summarized on disposition and baseline characteristics. Output will be summarized by study period (pre-period vs. post-period). All data listings will be reported for the enrolled set unless specified in Section 5.2.

Full Analysis Set

The full analysis set (FAS) population consists of all enrolled patients. Additionally, patients in the pre-period must receive at least one dose of antibiotics and patients in the post-period must receive at least one dose of dalbavancin for inclusion. All patients in the pre-period and post-period will be analysed. Data will be summarized by study period.

6.1.2 Sample size

An estimated 86 patients are anticipated to be enrolled at one US site. The sample size was initially estimated for a two-sided hypothesis test (two-sample equal-variance t-test) with a significance level of 0.05 comparing total hospital time (number of days) between the pre- and post-periods with 80% power. Assuming an average hospital length of stay of 4.0 days (inclusive of all enrolled subjects), with a standard deviation of 3.0 days, and a 2 day reduction in length of stay between the pre- and post-periods, it was estimated that 37 subjects in each arm of the trial (total enrollment of 74) would be required to demonstrate a mean reduction in hospital stay of 2 day. The final enrollment, including adjustments for attrition came to 86 subjects (43 patients in each period).

The average length of stay and variance for the site was determined after an estimated 25 subjects were enrolled in the pre-period. The sample size was confirmed with the interim analysis and the enrollment of 86 patients will be targeted.

6.1.3 Rounding

Means and medians will be rounded to one decimal more than that which the variable was recorded. Standard deviations will be rounded to two decimals more than that which the variable was recorded.

Percentages will be rounded to the nearest integer. Percentages for responses to a variable will only include patients with non-missing data, i.e. the denominator will be the number of patients with non-missing data.

P-values will be reported to three decimal places. Probabilities that are <0.001 will be presented as " <0.001 ."

6.1.4 Handling of outliers

Outliers will be examined using descriptive statistics, making sure that the minimum and maximum of the variable of interest are not unusually small or large and that the standard deviation seems appropriate for the data. If an outlier(s) is detected (e.g; more than 3 SD from the mean), the accuracy of the entry of the data point(s) will be verified (when possible) and corrected if appropriate.

Potential outliers will be identified prior to any statistical analysis. The effect of the any outliers on the analysis will determined by the statistician. Outliers will be included in or excluded from the statistical analyses as appropriate.

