5.10 Potential Hy's Law cases

Every subject that meets potential Hy's law criteria,

- ALT or AST $\geq 3 \times \text{ULN}$ AND
- Total Bilirubin $\geq 2 \times \text{ULN}$ AND
- Alkaline Phosphatase $< 2 \times \text{ULN}$

occurring anytime from the time he or she signs the ICF for the trial until the final follow up visit, investigators will notify the sponsor immediately when all the above criteria have been met. A potential Hy's law case will be sent directly to the sponsor by emailing [contact] on an AE of Special Interest Form along with the SAE Report Form as soon as possible (within 24 hours of learning of the potential Hy's law). The CRF for potential Hy's law cases will be completed within seven calendar days. Every effort to determine the cause of the liver enzyme abnormalities will be made, and close monitoring will be initiated in conjunction with the medical monitor and in accordance with the FDA "Guidance for Industry: Drug Induced Liver Injury- Pre-Marketing Clinical Evaluation" July 2009.

6 Data analysis

Frequency and proportion of subjects deemed eligible and ineligible for study enrollment based on each of the inclusion/exclusion criteria will be summarized. The frequency and proportion of subjects who successfully complete the study, withdraw, were lost-to-follow-up, and who terminated the study early, will also be reported. Subject characteristics at baseline will be summarized and described for all enrolled subjects and compared between the pre- and post-periods. Site characteristics will also be described. Descriptive statistics (count, mean, standard deviation, range for quantitative variables, and counts and percentages for categorical variables) will be reported for all outcomes. The difference in study outcomes between the pre- and post-period will be assessed using appropriate statistical methods, accounting for study site, with adequate power. The primary outcome will be tested for simple superiority, and subsequently, tested for non-inferiority with a 10% margin between the pre- and post-periods.

The primary analysis of differences in LOS is performed using a 2-sided hypothesis test of the modified intent-to-treat principle such that all evaluable patients are included in the analysis. Patients are evaluable if they received at least one dose of antimicrobial therapy for their ABSSSI. Differences in length of stay are measured by Mann-Whitney U test.

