6.2.4 Outcomes

6.2.4.1 Primary Outcomes

Primary Outcome: Infection-related Total Admitted Hospital Days

Infection-related total admitted hospital days will be calculated by two methods for the FAS population. First, LOS will be calculated by inpatient only stays and second, LOS will be calculated by inpatient stays including time spent in prolonged observation status (> 1 day). Descriptive statistics for the primary

[REDACTED]

outcome will be shown in a table by initial care, follow-up, and overall for the pre-period and post-period, and depicted graphically overall using box plots. Patient counts and percentages will be given for the primary outcome (e.g., 0 day, 1 day ... > 5 days). Descriptive statistics in the table will be repeated by all patients and patients who complete the study for comparison.

The primary analysis will consist of Hypothesis testing using a two sided (two sample equal-variance) t-test, with a significance level of 0.05, comparing the difference in total time (in days) spent in hospital between the pre- and post-periods. Violations of assumptions for the t-test in the data will be checked for. An appropriate alternative method will be selected if a major violation to an assumption is present, such as the Mann-Whitney U test². Overall differences in descriptive statistics between the pre- and post-periods for infection-related total admitted hospital days will be reported.

Because the baseline characteristics of the pre-period may differ from those of the post-period, a secondary analysis using a multivariate regression analyses, specifically a generalized linear mixed model (GLMM), [REDACTED]. As the outcome is expected to be heavily right skewed, the number of hospital days will be modeled assuming a negative binomial distribution with log link. If the model does not converge or fit, an alternate distribution will be selected. This model will assume mutual independence between the sites. Similar to above, the multivariate analysis will be completed for the primary outcome for inpatient stays only as well as including time spent under observation, as well as for all patients and patients who complete the study for comparison.

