Primary and Secondary Outcomes (All visits)	Hospitalization LOS (days)	
For all-cause: Σ (Hospitalization end date – Hospitalization start date +1), when both dates are available. If ongoing at end of study or discontinuation date, use study completion date or discontinuation date as end date. For outcomes, LOS will be computed two ways: only inpatient hospitalizations visits and inpatient hospitalizations visits with prolonged observation status (e.g., time in observation status exceeds 1 day). For infection-related:

[figure not shown]
Analysis Section (Visit)	Variable (Units)	Definition
		Subset all-cause hospitalization time for patients with infection-related hospitalization stays
Primary and Secondary Outcomes (End of Study Visit)	Completers Flag	
If "Did the patient complete the study?" = 1 on the end of study visit CRF page and date of study completion does not equal missing, then =Yes, Else = No
 
This flag will be used to repeat certain primary and secondary outcomes that could be influenced by early discontinuation (e.g., LOS)

Secondary Outcomes (Follow-up)	Response to Therapy at End of Therapy Visit	
The response will be categorized as a "Complete Response" if at the day 10-14 visit there is a reduction in pain or no pain, tenderness, nor fever and the primary lesion area has reduced in size.
 
Else, the response will be categorized as a "Partial Response" if at the day 10-14 visit there is a reduction in pain score or no pain, tenderness, nor fever and the primary lesion area remained the same size.
 
Else, the response will be categorized as a "Failure."

Secondary Outcomes (Follow-up)	WPAI	Scores and coded variables will be derived as described in Appendix D.
Secondary Outcomes (Initial Care and Follow-up)	SF-12	SF-12 sub-scores and total scores will be compiled using the Health Outcomes Scoring Software 5.0 by QualityMetric Inc. Further detail is given in Appendix E.
Adverse Events (Baseline, Initial Care and Follow-up)	Highest severity AE	Severity of most severe AE for the patient with order of severity: Severe>Moderate>Mild Patients who only have AEs reported with missing severity,

Analysis Section (Visit)	Variable (Units)	Definition
		highest severity AE will be reported as missing

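### SAP 6.1.4 lets verified long stays be left out of the primary length-of-stay test by judgement; they should stay in, and one LOS version should be named primary

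*SAP*

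**What the plan says.** SAP 6.1.4 sets out several steps. Ranges and SDs are inspected. An entry that looks extreme, with distance beyond 3 SD given only as an example, is checked where possible and corrected if wrong. On timing, "Potential outliers will be identified prior to any statistical analysis". Then "The effect of the any outliers on the analysis will determined by the statistician", and finally "Outliers will be included in or excluded from the statistical analyses as appropriate". The section covers any variable and does not exempt the primary outcome.

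Two statements point the other way. Protocol section 6 (Data analysis) describes a modified intent-to-treat primary analysis in which "all evaluable patients are included in the analysis". SAP 6.1.1, defining the full analysis set (FAS), says "All patients in the pre-period and post-period will be analysed".

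On the outcome itself, SAP 6.2.4.1 states that "LOS will be calculated by inpatient only stays and second, LOS will be calculated by inpatient stays including time spent in prolonged observation status", and Appendix B repeats that "For outcomes, LOS will be computed two ways". The 0.05 t-test is then described only as a comparison of total days in hospital. For the adjusted model, "the multivariate analysis will be completed for the primary outcome for inpatient stays only as well as including time spent under observation". SAP 6.2 makes no multiplicity adjustment.

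**The concern.** Error correction has its own step, so the final sentence of 6.1.4 can only add something if it reaches values that were checked and found true. For LOS, such a value is a real long stay, and SAP 6.2.4.1 itself expects the outcome to be strongly right-skewed. There is no criterion for keeping or dropping a value, no statement whether flagging is pooled or by period, no blinding to period, and no required run with and without the flagged values. Identification is timed before analysis; the decision to exclude is not timed.

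At stake are the size of the primary test and the estimated difference in days, which is the primary objective. A lesser gap of the same kind is that the SAP text does not say which of the two LOS versions the 0.05 test uses.

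**Working it through.** **1. The plan's own figure.** Inputs from SAP 6.1.2: two-sided alpha 0.05, power 80%, difference 2 days, SD 3 days. Normal approximation: n = 2(1.96 + 0.842)² × 3²/2² = 35.3, so 36 per period. The noncentral t calculation needs 36.3, so 37, as stated. Power is 80.8% at 37 and 86.3% at 43 per period. The sample size reproduces and is not at issue.

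**2. Where the example threshold falls.** 4 + 3×3 = 13 days at a mean of 4; 2 + 3×3 = 11 days at a mean of 2. Both lie well inside the 44-day window, so genuine stays can be flagged. One 30-day stay among 43 patients, the others averaging 4 days, moves the period mean by (30 − 4)/43 = 0.60 day, against a planned effect of 2 days.

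**3. Error rate with no effect.** Simulation of 20,000 trials, 43 per period, mean 4 and SD 3 in both periods, equal-variance t-test at 0.05. The four skewed shapes are assumptions: negative binomial (NB), 1 + NB, gamma and lognormal. Monte Carlo standard error is about 0.2 points. Entries are percentages of trials.

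| | NB | 1 + NB | Gamma | Lognormal |
|---|---|---|---|---|
| Any value beyond 3 SD, pooled | 70.5 | 86.4 | 83.3 | 95.0 |
| Reject, all values kept | 4.89 | 4.70 | 4.76 | 4.81 |
| Reject, fixed pooled exclusion | 5.05 | 4.76 | 5.00 | 5.03 |
| Reject, fixed within-period exclusion | 7.30 | 7.80 | 7.88 | 8.44 |
| Smaller p of keep or drop, pooled | 6.56 | 6.74 | 6.90 | 7.46 |
| Smaller p of keep or drop, within period | 7.80 | 8.42 | 8.48 | 9.22 |

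**4. Estimated difference when the true difference is 2.0 days** (pre-period mean 4, SD 3; post-period mean 2). The plan gives one SD of 3. The alternatives are assumptions: 1.5 = 3 × 2/4 (constant coefficient of variation) and 2.12 = 3 × √(2/4) (variance proportional to the mean).

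| Exclusion, post-period SD | NB | 1 + NB | Gamma | Lognormal |
|---|---|---|---|---|
| Pooled, 3 | 2.04 | 2.07 | 2.02 | 1.95 |
| Pooled, 2.12 | 1.81 | 1.81 | 1.78 | 1.77 |
| Pooled, 1.5 | 1.72 | 1.66 | 1.68 | 1.64 |
| Within period, 3 | 2.16 | 2.23 | 2.15 | 2.09 |
| Within period, 1.5 | 1.92 | 1.95 | 1.93 | 1.88 |

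The shrinkage with pooled flagging arises because the values removed are nearly all pre-period. At a post-period SD of 1.5, an average of 1.32–1.62 pre-period values and 0.00–0.11 post-period values are dropped per trial.

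**5. LOS version.** Section 6.2.4.1 lists inpatient-only first, Appendix B ranks neither, and the title of Table 7 in SAP 7.0 names neither. Either version fixed in advance gives about 5% (4.6–5.2%). Taking the better of the two gives 5.9–7.1% if 10–50% of patients have 2–3 observation days, and 6.6–9.2% if 5–50% of stays are wholly observation. It gives 5.4–5.9% if 5–10% of patients are affected and inpatient stay cannot fall below about one day. The documents give no observation share, so these only bracket the size.

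**The case against.** The case on the other side is substantial. In 6.1.4 the 3 SD figure is an example that prompts data checking; it is not an exclusion rule. The section speaks of a single mean, which reads more naturally as pooled than as by period, and fixed pooled exclusion keeps the test at about 5%. At the plan's own equal SD of 3, pooled exclusion is also nearly unbiased (1.95–2.07). Where it does bias, at a post-period SD of 1.5, the bias is towards no effect and power after exclusion stays at 96–99%. Listing 9 shows LOS for the Enrolled Set, and the planned summaries include minimum, maximum and counts by day, so a dropped stay could be traced. All of this stands, and it makes the harm conditional. It does not supply a rule: traceability comes after the fact, and early identification does not fix the later decision.

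A reader might infer more in four ways, and the documents do not support it:

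- **That 6.1.4 flatly contradicts the all-patients statements.** Those mainly define who belongs to the analysis population, while 6.1.4 is a general paragraph about values. It is a tension.
- **That the SAP plans to decide on exclusion after seeing the result.** It does not say so; it only fails to rule it out.
- **That no LOS version is designated anywhere.** The table shells were not available, and the wording leans towards inpatient-only: the outcome is named in terms of admitted days, and that version comes first.
- **That the unquantified switch from the t-test to Mann-Whitney is a similar threat.** A switch driven only by the shape of the data gives 4.8–5.4%, about nominal, so it is no part of this point.

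**Conclusion.** The point holds as a gap worth closing in the primary analysis. SAP 6.1.4 permits true long stays to be removed from the primary test without a criterion, in a setting where 71–95% of simulated null trials would have at least one candidate.

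The size depends on what is done. Keeping all values, or always applying a pooled cut, leaves type I error at about 5%. A fixed within-period cut gives about 7–8.5% even when chosen honestly in advance, and a choice made after the result gives about 6.5–9%. A pooled cut reduces a true 2.0-day difference to about 1.65–1.8 days, but only if the post-period SD is below the planned 3. These figures rest on assumed skewed shapes and, for the bias, on assumed SDs; they indicate size only.

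The undesignated LOS version is a true but secondary gap. Its effect on error arises only if the version is picked with results in view, and its size cannot be settled from the documents.

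**What to change.** In SAP 6.1.4, state that every verified LOS value stays in the primary FAS test, that only documented data errors are corrected, and that any run excluding outliers is a labelled sensitivity analysis.

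In SAP 6.2.4.1, designate one LOS version for the 0.05 test before the periods are compared. Inpatient-only is the one the present wording suggests, with inpatient plus prolonged observation as the sensitivity version. If the table shells already designate one, carry that into the text.

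The cost is SAP wording and a small loss of flexibility. N stays at 43 per period, and with all values kept and one version named the primary test runs at about 5%.
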